## Abstract

**Background:** A large portion of Afghanistan's population, particularly children, has endured prolonged conflict, poverty, and displacement, leading to significant psychological distress. As children grow into adolescence and adulthood, this distress often manifests in mental health symptoms and an increased likelihood of violent behaviours. With limited mental health professionals and strong stigma around mental health in Afghanistan, culturally adapted, evidence-based interventions are needed.

**Objective:** The study aims to explore the feasibility and acceptability of culturally adapted mental health intervention Problem Management Plus with an additional Emotional Processing module (PM+ EP), in reducing psychological distress in young Afghans. The primary objective is to assess the feasibility of delivering this intervention in Afghanistan and its acceptability by the target communities, and the secondary objective is to assess symptom reduction and behavioural change.

**Methods:** This is a pilot Randomized Control Trial (RCT) with participants aged 16 to 30 in Afghanistan. Eligible participants, young Afghans with high levels of distress and impaired functioning - measured by the Kessler Psychological Distress Scale (K10) -, will be randomized to PM+ EP (n=30) or the waiting group (n=30). The participants will be evaluated through self-report questionnaires at three time points; baseline (T1), four weeks later immediately post-intervention (T2), and 3 months post-intervention (T3), and through a qualitative interview (Process Evaluation) at the end of the study. Outcomes will include measures of anxiety and depression (HSCL-25), aggressive behaviours (AGQ), PTSD symptoms (PCL-5), and daily functioning (WHODAS 2.0).

**Results and Conclusion:** This study will assess the feasibility and acceptability of culturally adapted PM+ EP in Afghanistan and explore the relationship between mental health symptoms and violence among young Afghans. It will be the first to evaluate the feasibility of PM+ EP with this population and could pave the way for a large define RCT examining the effectiveness this approach, should the results show promise.

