## Highlights

- Examine the feasibility and acceptability of culturally adapted PM+ EP among young populations with high levels of distress in Afghanistan.
- Assess mental health symptoms reduction and behavioural change among Afghan youth.
- Discuss the process of culturally adapting evidence-informed mental health interventions for Afghan populations.

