
This pilot study will assess the feasibility, acceptability, and safety of implementing the culturally adapted PM+ EP among a novice population in Afghanistan. The study will examine the process of cultural adaptation and implementation, evaluating whether these interventions are practical and well-received by the target population. As a secondary objective, the study will explore the association

between mental health symptoms—such as depression, anxiety, aggression, and impaired functioning—and experiences of violence among young people in Afghanistan. Using our chosen instruments, we can examine key factors contributing to violence at baseline and explore how differences in mental health outcomes relate to behavioural change. Ultimately, the findings may inform the development of scalable mental health interventions that support improved mental health outcomes, daily functioning, and a reduction in violence.

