## 2. Methods

### 2.1 Design and Setting

The study is a stand-alone project, culturally adapting the existing World Health Organization (WHO) PM+ programme and trialling it with a new subject population - Afghan youth. This pilot RCT will be conducted in a community setting in Afghanistan and the research team will be a mix of researchers attached to the Vrije Universiteit (VU) Amsterdam, and field researchers in Afghanistan working with non-profit Peace of Mind Association (PoMA).

This study is a pilot randomized controlled trial (RCT) which involves assessing the feasibility and acceptability of culturally adapted PM+ with an Emotional Processing (EP) module (PM+ EP), and exploring the relationship between mental health symptoms and behavioural change. Self-report assessments will be conducted at three points during the study; prior to delivering the intervention (T1), directly post-intervention (T2), and 3 months-post intervention (T3), and through a qualitative interview conducted at the end of the study.

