### 2.3.3 Outcomes

In this pilot RCT, the primary outcome is to explore the feasibility and acceptability of delivering the PM+ EP intervention in Afghanistan. The study serves to demonstrate whether such interventions could be safely scaled and produce positive outcomes for the target population. The study's secondary outcome is to analyse the relationship between mental health and violence, and to discuss the potential for impact of culturally adapted mental health programming on symptom-change and behavioral change, in particular in reducing violence, and to illustrate the context-specific linkages between mental health and violence. Through this research, we can examine the mental health symptoms, risk factors, and functional impairment, caused by ongoing exposure to conflict or adversity, and advocate for scaling-up adaptation and implementation of evidence-informed mental health interventions in countries such as Afghanistan.

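### The secondary aim is change in symptoms and behaviour in the Abstract and Highlights, but a link between mental health and violence in sections 1 and 2.3.3; these are different quantities

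*Protocol*

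**What the plan says.** Four places in the protocol set out or restate the secondary aim.

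- **Abstract, Objective:** "the secondary objective is to assess symptom reduction and behavioural change".
- **Highlights:** "Assess mental health symptoms reduction and behavioural change among Afghan youth".
- **Section 1, closing paragraph:** "As a secondary objective, the study will explore the association" between symptoms and experiences of violence. The stated approach is to "examine key factors contributing to violence at baseline and explore how differences in mental health outcomes relate to behavioural change".
- **Section 2.3.3:** "The study's secondary outcome is to analyse the relationship between mental health and violence". The same sentence goes on "to discuss the potential for impact of culturally adapted mental health programming on symptom-change and behavioral change".

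Two further places bear on the aim without labelling it secondary. The Abstract's Results and Conclusion says that the study will "explore the relationship between mental health symptoms and violence among young Afghans". Section 2.1 describes the design as "exploring the relationship between mental health symptoms and behavioural change".

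Section 3 plans mean differences in subscale and total scores between T1 and each of T2 and T3. It assigns the linear mixed model, which carries treatment as a fixed effect, to the feasibility and acceptability data.

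**The concern.** In the Abstract and Highlights the target is change: do symptoms fall, and does behaviour shift? In section 1 and the first part of section 2.3.3 the target is a relationship between two variables: do people with more symptoms also have more to do with violence? In a randomised trial the first question calls for a comparison of arms. The second can be answered without using the randomisation.

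What is at stake is which quantity the secondary result will be. As written, a reader cannot tell whether it is a randomised estimate of what PM+ EP does to symptoms and aggression, a within-person change, or an association that allocation plays no part in. Whoever writes a statistical analysis plan from this protocol would have to choose among them.

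**Working it through.** There is no figure to reproduce. Section 2.2.2 states that no power calculation was made, and the protocol gives no significance level, effect size or expected correlation. The check is therefore a comparison of the statements.

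| Place | Labelled secondary? | Quantity | Time point stated there |
|---|---|---|---|
| Abstract, Objective | Yes, as the only one | Change in symptoms and behaviour | None |
| Highlights | No | Change, as in the Abstract | None |
| Section 1 | Yes, as one such objective | Association of symptoms with experiences of violence; also how outcome differences relate to behavioural change | Baseline for the factors contributing to violence; none for the rest |
| Section 2.3.3 | Yes, as the study's secondary outcome | Relationship between mental health and violence analysed; impact on change discussed | None |
| Section 2.1 | No | Relationship between symptoms and behavioural change | None |
| Section 3 | No | Mean score differences from T1 to T2 and T3 | T1, T2, T3 |

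**Step 1: are the quantities the same?** Write S for a symptom score and V for a violence or aggression score.

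- Association at baseline: corr(S, V) at T1. Section 2.1 places T1 before the intervention is delivered, so this quantity contains no information on the effect of PM+ EP.
- Within-person change: mean(S at T2) − mean(S at T1). In the PM+ EP arm this equals the treatment effect plus whatever change would have occurred anyway.
- Between-arm difference: mean change in PM+ EP − mean change in the waiting group. The change expected without treatment is the same in both arms on average and cancels, leaving the treatment effect.

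These are three different quantities, and only the third isolates the effect of the intervention. A correlation between the change in S and the change in V does not isolate it either: the two can move together within people when the arms do not differ on average.

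**Step 2: does section 3 decide between them?** It does not. For the scores it gives the within-person quantity. The one model with a treatment term is described as serving retention, attendance and adherence. No analysis of the relationship between symptoms and violence is named. That last omission could be supplied in an analysis plan that is not shown, so it is not counted as a fault; it means only that section 3 cannot break the tie.

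**Step 3: can the design deliver the between-arm quantity?** Yes. Section 2.3 has all participants complete the four instruments at T1, T2 and T3. Section 2.2.2 assigns 30 to each arm and offers the intervention to the waiting group only after the study. The comparison is therefore available at both T2 and T3 from data already planned.

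**The case against.** The strongest reply is that this is one compound aim, loosely worded. Section 1 uses the indefinite article, which leaves room for another secondary objective. It also goes beyond baseline, to how outcome differences relate to behavioural change. Section 2.3.3 carries both strands in one sentence, and the Abstract's conclusion mentions the relationship as well. Section 2.1 never calls its wording secondary, so it should not be counted as a rival definition.

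Most of this stands, and it narrows the point. The clear mismatch is the Abstract and Highlights against section 1 and the first part of section 2.3.3. It does not remove the point. The Abstract and section 2.3.3 each speak of a single secondary aim and name different ones, and section 2.3.3 reverses the Abstract's priority by analysing the relationship and only discussing impact. If both aims are intended, they need separate labels.

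A reader might infer more: that the secondary objective could be achieved with an ineffective treatment, or that the authors could report the more favourable version and offer an association as grounds for a larger trial. The documents do not support this. The aims are to assess and explore, with no success threshold. No passage makes the association a criterion for progression. The Abstract's remark about promising results closes a sentence on feasibility, and section 5 makes further implementation depend on the intervention being feasible and acceptable.

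**Conclusion.** The inconsistency is real and can be shown from the protocol text alone. The secondary aim is a change in two places and, in two others, mainly an association that cannot show whether PM+ EP alters symptoms or behaviour; the analysis section does not reconcile them.

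The weight is minor to moderate. This is a pilot whose primary aim is feasibility and acceptability, and neither that aim nor any sample-size figure is affected. The size of the fault cannot be put as a number: it lies in which quantity is meant, and the protocol states no test, threshold or expected value against which to measure it. The conclusion rests on one assumption, that the symptom and behaviour change of interest is change due to the intervention, as the Abstract's objective of exploring PM+ EP for reducing distress implies.

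**What to change.** Use one wording in the Abstract, the Highlights and sections 1 and 2.3.3, and align section 2.1 with it.

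1. **Secondary objective on symptom and behaviour change:** the between-arm difference in HSCL-25, PCL-5, WHODAS 2.0 and AGQ at T2 and at T3, in all randomised participants, reported as estimates with 95% intervals.
2. **Association between symptoms and violence:** a separately labelled objective, with a statement that it is not evidence of an intervention effect. Whether it is called exploratory or a second secondary objective is the authors' choice; either removes the inconsistency.
3. **Section 3:** attach the between-arm comparison of the scores to the first objective, so that the treatment term is not confined to feasibility and acceptability data.

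The cost is wording in five places and one sentence in section 3. No new data, visits or participants are needed. If the association is labelled exploratory, it loses its present secondary standing.

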#### 2.2.2 Sample Size

Since this is a pilot RCT no power calculations have been carried out. The total sample size will be 60 persons, with half of the participants receiving PM+ EP (N=30) and half assigned to the waiting group (n=30). Randomization will be carried out using a random numbers table generated by computerised software. Those participants in the waiting group will be offered the chance to receive the intervention

post-study. The total number included in the study allows us to evaluate the feasibility and acceptability of the intervention and allow for drop-out rates and incomplete data to be omitted. For the Process Evaluation, a non-random sample size of ten people will be interviewed.

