### 2.3 Procedure

Participants receiving PM+ EP will meet their facilitator individually, someone of the same gender, and receive the intervention through sessions conducted over Zoom or a similar platform; mitigating the difficulties around accessing psychological support, and the risks associated with safety of participants and stigma around mental health. Participants will receive six individual sessions of PM+ EP over the period of one calendar month.

All participants will complete four surveys for assessment at study points T1, T2 and T3; The Hopkins Symptom Checklist 25 (HSCL-25) to measure for anxiety and depression (Mollica et al, 1987), The Aggression Questionnaire (AQG) to measure violent behaviours (Buss and Perry, 1992), The Post Traumatic Stress Disorder (PTSD) Checklist for DSM-5 (PCL-5) will screen participants for symptoms of PTSD (Weathers et al, 2013), and cognitive ability and overall ability to function will be measured by WHO Disability Assessment Schedule 2.0 (WHODAS 2.0) (WHO, 2012). The latter has been used in studies looking at PTSD and other trauma-symptoms in low-resource settings, to assess the communities' impaired daily functioning (Hamdani et al., 2020). After the final assessment has been complete, a non-random sample of participants will be invited to partake in an interview – the Process Evaluation -, to gather qualitative data to assess the feasibility and acceptability of the program.

The timeline and frequency at which the instruments that will be used for screening, baseline and post intervention are listed in the table below. Some of the listed instruments have translations in Dari or Farsi (Afghan Persian/Iranian Persian). In case there is no translation, the instrument will be translated and back translated by the research team.

*Table 1. Measure Overview and Timeline*

Assessment Timeline					
Enrolment T0	Allocation	Baseline T1	Post-intervention T2	Follow-up - 3 months Post- intervention T3	Close-out
Enrolment:					
Eligibility criteria	X				
Informed consent	X				
Allocation		X			
Intervention:					
PM+ EP		X	X	X	X
Waiting Group					
Assessment:					
K10	X				
HSCL-25		X	X	X	
AGQ		X	X	X	
DSM-5 (PCL-5)		X	X	X	
WHODAS 2.0		X	X	X	
Process Evaluation					X

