### 2.3.2 Process Evaluation

After the study, participants will be approached for the Process Evaluation; sampling five people ensuring variance on gender, age, and completion of the program (drop out/completed), to partake in a qualitative interview. Five mental health providers who delivered the intervention PM+ EP will also be approached to participate in the qualitative interviews. The objective of this process is to understand the perspectives of those who received the intervention and those who delivered the intervention, on the feasibility and acceptability of the program among their own communities and in their country, and the perceived change in mental health symptom and behavioural change for themselves or the participants. This will provide insight into the possibility of scaling the study and providing the intervention on a wider scale. The Process Evaluation will use a semi-structured interview script to collect qualitative data, and participants will be asked about their experiences with the intervention, ease of adherence to the intervention, thoughts on the recruitment process, the PM+ EP facilitators and their approach, and whether the program could be effectively integrated into health systems in Afghanistan.

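### Does dating T3 from the end of the intervention leave the waiting group without an assessment date?

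*Protocol*

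**What the plan says.** The protocol gives the assessment times in three places.

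- **Abstract, Methods:** "baseline (T1), four weeks later immediately post-intervention (T2), and 3 months post-intervention (T3"). The subject of the sentence is the participants in general, and the preceding sentence has just described both arms.
- **Section 2.1:** "prior to delivering the intervention (T1), directly post-intervention (T2), and 3 months-post intervention (T3"). There is no interval from baseline or randomization.
- **Section 2.3, Table 1 header:** "Follow-up - 3 months Post- intervention T3". T2 is labelled only as post-intervention.

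Section 2.3 applies the schedule to both arms: "All participants will complete four surveys for assessment at study points T1, T2 and T3". It also gives the length of the course: "Participants will receive six individual sessions of PM+ EP over the period of one calendar month". Section 2.2.2 deals with the other arm: "Those participants in the waiting group will be offered the chance to receive the intervention", and places this after the study. Section 3 takes mean changes from T1 to T2 and T3, and section 2.5.2 counts assessment completion among the feasibility measures.

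**The concern.** Read literally, a T3 counted from the end of the intervention has no starting point in an arm that receives no intervention before T3. That arm is 30 of 60 participants, half the trial. T2 has a calendar value usable in both arms only in the Abstract, not in the Methods text or the table that field staff would work from.

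Two consequences could follow. First, if changes from baseline are compared between arms, elapsed time might differ by arm. An event-based date moves with late or overrunning sessions in the PM+ EP arm while the waiting group has nothing to move with. Early stopping is foreseen: section 2.2.2 chose the sample size to "allow for drop-out rates and incomplete data to be omitted", and section 2.3.2 samples interviewees by "completion of the program (drop out/completed"). Second, a waiting-group T3 without a due date is harder to classify as completed, late or missed.

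**Working it through.** **Inputs from the protocol.** Arms of 30 and 30, total 60 (section 2.2.2). T2 four weeks after T1, that is 28 days (Abstract). Course of one calendar month, that is 28 to 31 days (section 2.3). T3 three months post-intervention (Abstract, section 2.1, Table 1).

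**Assumptions.** The first session takes place at T1, and three months is 91 days.

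**Step 1: the protocol's own figure.** 30 + 30 = 60, as stated. The waiting group is 30/60 = 50%.

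**Step 2: reading the three places together.** The Abstract uses a single phrase for T2 that is both four weeks after baseline and immediately post-intervention. The two descriptions therefore mark the same point, and the course length in section 2.3 agrees with this to within a few days. Section 2.1 and Table 1 repeat the label without the interval; they do not give a different one. So T2 = T1 + 28 days and T3 = T2 + 3 months for everyone.

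**Step 3: size of the gap on the stated schedule.**

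| | PM+ EP, timed from end of course | Waiting group, timed from four-week T2 | Difference |
|---|---|---|---|
| T2 | day 28 to 31 | day 28 | 0 to 3 days |
| T3 | 28 + 91 = 119 to 31 + 91 = 122 | 28 + 91 = 119 | 0 to 3 days |

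The largest difference is 3/119 = 2.5% of the follow-up time. Two of the four questionnaires, the PCL-5 and the WHODAS 2.0, look back over about a month (section 2.5.3), so a shift of up to three days changes little of what they measure.

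If three months is counted by the calendar over all start dates in a year, T3 falls 117 to 120 days after T1 from a four-week T2, and 117 to 123 days from a one-calendar-month T2. The picture is the same.

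**Step 4: what larger gaps require.**

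- *Start lag of 7 days (assumed).* The course ends on day 7 + 28 = 35 to 7 + 31 = 38, which is 7 to 10 days after a four-week T2.
- *Stopping after session 3 of 6, timed from the last session received (assumed, with equal spacing).* Spacing is 28/5 = 5.6 to 31/5 = 6.2 days. Session 3 falls on day 2 × 5.6 = 11.2 to 2 × 6.2 = 12.4, which is 28 − 11.2 = 16.8 to 28 − 12.4 = 15.6 days before the waiting group's T2. T3 falls on day 102.2 to 103.4 against 119, the same gap.
- *Stopping after session 5, same assumptions.* Day 4 × 5.6 = 22.4 to 4 × 6.2 = 24.8, so 5.6 to 3.2 days early.
- *Counting the waiting group's three months from T1.* T3 falls on day 89 to 92, about four weeks earlier than 117 to 120.

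The protocol states neither a lag nor even spacing. Timing an early stopper from the last session received would contradict the Abstract's four-week T2. Counting three months from T1 contradicts all three statements of T3.

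**The case for a change.** The strongest case for a change is that assessment dates tell staff when to collect data, so they belong in the protocol and cannot be left to the statistical analysis plan. Here the protocol fixes T3 three times with an anchor that one arm lacks, and the only calendar value sits in the Abstract. Someone working from section 2.1 and Table 1 alone might guess, and the wrong guess could cost about four weeks. One sentence would remove the doubt.

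Part of this stands. No passage gives T3 as an interval from baseline, and the rule for the waiting group has to be inferred. But the inference takes one step, and no other reading fits the text.

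The natural remedy, a fixed date from baseline that holds whatever the session dates, is not free either. With a 7-day start lag, a T2 fixed at day 28 would fall 7 + 28 − 28 = 7 to 7 + 31 − 28 = 10 days before the last session, so treated participants would be assessed before finishing. Moving T2 to day 31 to cover the longest month would depart from the Abstract's four weeks and still fall 7 + 28 − 31 = 4 to 7 + 31 − 31 = 7 days before the last session. An event anchor keeps T2 truly post-intervention; a calendar anchor keeps elapsed time equal. Either is a fair choice.

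The feasibility argument is the weaker one. Assessment completion can be counted as a T3 questionnaire returned or not returned, without an exact due date. Windows for an on-time visit are commonly set in an operations manual or the analysis plan.

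**Conclusion.** The concern describes the wording correctly but does not call for a change. The protocol leaves implicit that T3 is three months after T2 in both arms. The Abstract supplies what is needed to infer it, and the Methods do not contradict it. Followed that way, assessment times differ between arms by 0 to 3 days over about four months.

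That figure rests on sessions starting at T1, delivery within one calendar month, and three months taken as 91 days. The gaps of 7 to 10 days and of about 16 to 17 days need a start lag, equal session spacing or last-session timing, none of which the protocol states. The between-arm comparison that would be affected concerns secondary symptom and behaviour outcomes in a pilot with no power calculation, and section 3 does not say explicitly that the mean changes are to be compared between arms. This is a gap that the trial team would fill sensibly when drawing up the visit calendar.
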